5.3 Description of events

Diagnosis-type medical events following MenACWY-CRM exposure in children 2-23 months of age will be described if five or more of a diagnosis or diagnosis grouping are observed. Medical events will be reviewed and summarized, at least including age at vaccination, gender, age at diagnosis, MenACWY-CRM vaccination history, setting of diagnosis, and if available, underlying condition of vaccination. Recurrence of the same medical event after repeated MenACWY-CRM vaccination of the same person will be included in the description as well. See Appendix A, Table Shell 6 for details.

5.4 Sensitivity analysis

No sensitivity analyses are planned.

6. STATISTICAL CONSIDERATIONS AND LIMITATIONS

6.1 Statistical considerations

Due to the expected small sample size, no formal hypothesis testing or statistical analysis is planned.

6.2 Internal Validity

Misclassification of diagnosis

As this study focuses on medical events requiring hospitalization and emergency care among children 2-23 months of age enrolled as KPSC health plan members, it is unlikely that serious and acute outcomes would be missed or misclassified. Also, due to the ICD-9 to ICD-10 transition, both ICD-9 and ICD-10 codes may need to be searched to exclude pre-existing conditions. Some pre-existing conditions may be missed from the automated search due to imperfect mapping between ICD-9 and ICD-10.

Misclassification of exposure

Depending on the available data in the medical record database on the recording of a vaccination, it may be that not all vaccinations are given through the HMO, resulting in not all vaccination data being present in the medical record. As vaccinations are available at no cost to members of the HMO, we expect that very few vaccinations will be received outside of the HMO. However, loss of these data should not affect results because analyses are confined to those individuals with a recorded vaccine administration.

Missing Data

No imputation will be performed. We expect there to be a very low rate of missing data regarding population characteristics, such as age and gender, and diagnoses. The study uses EMRs as the source of information for diagnoses, so events that do not result in a medical visit may be missed. Subjects missing the stratification factors will be excluded from subgroup analysis where the stratification factor is unknown. We expect that most vaccines will be captured by the EMR, with very little missing information. It is possible that some study subjects will have received meningococcal vaccine prior to joining the health plan, and these prior doses may not be captured. This number is expected to be small and not to have a material impact on the results.

Handling of Loss to Follow-up

We expect there to be minimal loss to follow-up due to the high retention of KPSC health plan members in this age group. Any loss will be addressed in the data analysis by the truncation of person-time in the event rate calculation.

7. STUDY REPORT

The final report will include all data generated from this study as specified in this SAP.

8. LIST OF REPORT TABLES, LISTINGS AND FIGURES

	Population* (all or per event)	Description	Strata**
Table 1	All	Study population selection	
Table 2	All	Baseline Characteristics of MenACWY-CRM recipients 2-23 months of age	Number of vaccinations received
Table 3	All	Follow-up characteristics of MenACWY-CRM recipients 2-23 months of age	Number of vaccinations received
Table 4	Per event	Summary of event identification and review	
Table 5	Per event	Frequency and rate of events among infant MenACWY-CRM recipients	Number of vaccinations received, care setting (5b only), recurrence (5b only)
Table 6	Per event	Description of diagnoses among infant MenACWY-CRM recipients	
Figure 1	All	Vaccinations by Month	Number of vaccinations received

*All = all MenACWY-CRM recipients,

Per event will include all recipients with no history of that event prior to the first MenACWY-CRM dose

** Data are only presented in stratum if sufficient numbers are available in each stratum ($n \geq 5$).

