5.1 Identification and review of events

Medical events occurring in ED and inpatient settings within 6 months following a MenACWY-CRM vaccination will be searched in the EMR.

Medical events will be characterized two ways: by encounter (hospitalization only, ED only, or both ED and hospitalization) and by diagnosis (see Appendix A, Table Shell 4 for details). The analysis allows for any recurrent events (i.e. different episodes of the same diagnosis) to be counted independently.

For characterization by encounter (Table 4a), all dates used for analysis will be the date of the ED encounter or hospital admission. Encounters will be considered pre-existing if all diagnoses made during the encounter are present in the medical record prior to the first dose of vaccine. Upon chart review by the study physician co-investigator, an encounter will be refuted if it is found to not be a true ED or hospital encounter. Each encounter will be reported as a single event, regardless of the number of diagnoses made during the encounter.

For characterization by diagnosis (Table 4b), all dates used for analysis will be the first date that the diagnosis is recorded in the EMR in any medical setting. A diagnosis will be excluded as pre-existing if the same ICD diagnosis code appears in any medical setting prior to the first dose of MenACWY-CRM vaccination. A diagnosis will be considered refuted if, upon chart review by the study physician co-investigator, there is no evidence of the diagnosis in the medical record. Multiple diagnoses associated with the same episode will be identified, but only the first diagnosis date (in any setting) will be counted in the analysis of each episode. Subsequent diagnoses for the same episode will be marked in Table 4b as "Diagnosis is continuation of an ongoing episode." An episode will be considered as ended when there is symptom resolution as determined by chart review (e.g., symptoms stated to have resolved or the diagnosis/symptoms have been absent from the medical record before they are mentioned again). In the case of recurrent events, the date used will be the date of the first diagnosis in the medical record following resolution of the prior episode. Recurrent events will be marked in Table 4b as "Diagnosis is a recurrence". Each diagnosis will be described independently. It is possible that different diagnoses from the same inpatient or ED encounter could have different diagnosis

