Plan Prepared by: PPD, MS
Research Manager, Biostatistics
Kaiser Permanente Southern California

Version and Date: Version 2.0: 17 November 2015

Approvals

Approvers, Organization & Role	Approval Status	Date
PPD [REDACTED], MS KPSC Research and Evaluation Research Manager, Biostatistics	Approved	11/17/2015
PPD [REDACTED] KPSC Research and Evaluation Principal Investigator	Approved	11/17/2015
PPD [REDACTED] Department of Epidemiology GlaxoSmithKline Epidemiologist	Approved	11/17/2015

Publication Record

Version	Date	Primary Author	Description
1.0	September 18, 2015	PPD [REDACTED]	1 st Draft for GSK Review
1.1	October 16, 2015	PPD [REDACTED]	2 nd Draft for GSK Review
1.2	October 30, 2015	PPD [REDACTED]	Final draft for GSK Review
1.3	November 6, 2015	PPD [REDACTED] [REDACTED]	Comments on Draft 1.2
1.4	November 11, 2015	PPD [REDACTED]	Final draft for GSK Review
2.0	November 17, 2015	PPD [REDACTED]	Approvals obtained, SAP finalized

Definitions

Concomitant vaccination(s) – any other vaccination(s) administered to a subject on the same date as a MenACWY-CRM vaccination.

Day 0 - For the calculation of study day, Day 0 is the date when the index vaccination is received.

Event – Events are classified on an encounter level and a diagnosis level. For encounters, an inpatient admission, emergency department (ED) visit, or an ED visit resulting in an inpatient admission will each be treated as a single event. For diagnoses, all medical diagnoses made during ED and inpatient visits are considered events, which will be further classified as pre-existing, new, recurrent, or part of an ongoing episode.

Episode – Diagnosis-type medical events that result in multiple encounters during the observation period are considered episodes. Episodes comprise the course of a disease or condition, from initial presentation through resolution, as determined through chart review. An episode will be consolidated as a single event for analysis. For each episode, the first diagnosis date in any care setting will be used for analyses.

First-dose - no prior dose of a quadrivalent meningococcal conjugate vaccine recorded in the full medical history

Index vaccination – The first receipt of MenACWY-CRM at a KPSC facility between July 1, 2014 and June 30, 2017 in a study subject of which the date of administration defines the start of the observation period.

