5.1 Identification and review of events

Medical events occurring in ED and inpatient settings within 6 months following a MenACWY-CRM vaccination will be searched in the EMR.

Medical events will be characterized two ways: by encounter (hospitalization only, ED only, or both ED and hospitalization) and by diagnosis (see Appendix A, Table Shell 4 for details). The analysis allows for any recurrent events (i.e. different episodes of the same diagnosis) to be counted independently.

For characterization by encounter (Table 4a), all dates used for analysis will be the date of the ED encounter or hospital admission. Encounters will be considered pre-existing if all diagnoses made during the encounter are present in the medical record prior to the first dose of vaccine. Upon chart review by the study physician co-investigator, an encounter will be refuted if it is found to not be a true ED or hospital encounter. Each encounter will be reported as a single event, regardless of the number of diagnoses made during the encounter.

For characterization by diagnosis (Table 4b), all dates used for analysis will be the first date that the diagnosis is recorded in the EMR in any medical setting. A diagnosis will be excluded as pre-existing if the same ICD diagnosis code appears in any medical setting prior to the first dose of MenACWY-CRM vaccination. A diagnosis will be considered refuted if, upon chart review by the study physician co-investigator, there is no evidence of the diagnosis in the medical record. Multiple diagnoses associated with the same episode will be identified, but only the first diagnosis date (in any setting) will be counted in the analysis of each episode. Subsequent diagnoses for the same episode will be marked in Table 4b as “Diagnosis is continuation of an ongoing episode.” An episode will be considered as ended when there is symptom resolution as determined by chart review (e.g., symptoms stated to have resolved or the diagnosis/symptoms have been absent from the medical record before they are mentioned again). In the case of recurrent events, the date used will be the date of the first diagnosis in the medical record following resolution of the prior episode. Recurrent events will be marked in Table 4b as “Diagnosis is a recurrence”. Each diagnosis will be described independently. It is possible that different diagnoses from the same inpatient or ED encounter could have different diagnosis

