8. LIST OF REPORT TABLES, LISTINGS AND FIGURES

	Population* (all or per event)	Description	Strata**
Table 1	All	Study population selection	
Table 2	All	Baseline Characteristics of MenACWY-CRM recipients 2-23 months of age	Number of vaccinations received
Table 3	All	Follow-up characteristics of MenACWY-CRM recipients 2-23 months of age	Number of vaccinations received
Table 4	Per event	Summary of event identification and review	
Table 5	Per event	Frequency and rate of events among infant MenACWY-CRM recipients	Number of vaccinations received, care setting (5b only), recurrence (5b only)
Table 6	Per event	Description of diagnoses among infant MenACWY-CRM recipients	
Figure 1	All	Vaccinations by Month	Number of vaccinations received

*All = all MenACWY-CRM recipients,

Per event will include all recipients with no history of that event prior to the first MenACWY-CRM dose

** Data are only presented in stratum if sufficient numbers are available in each stratum ($n \geq 5$).

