Female	n (%)				
Underlying condition of index vaccine indication					
Persistent complement component deficiencies	n (%)				
Asplenia (functional, anatomic)	n (%)				
Unknown	n (%)				
Concomitant vaccinations	n (%)				
1 concomitant vaccination	n (%)				
≥ 2 concomitant vaccinations	n (%)				
vaccine 1	n (%)				
vaccine 2	n (%)				
Other*	n (%)				
Vaccinations <6 months prior to index	n (%)				
Any vaccination prior to index	n (%)				
vaccine 1	n (%)				
vaccine 2	n (%)				
Other*	n (%)				

* Includes all vaccines with less than 10 recipients

N/A = Not Applicable

† Any cell with count >0 but less than 3 is presented as "<<"

Table 3: Characteristics of MenACWY-CRM Recipients 2-23 Months of Age during the Observation Period

Characteristic	Total	Number of doses received			
		One	Two	Three	Four
MenACWY-CRM vaccination during observation period					
1 dose	n (%)				
2 doses	n (%)				
3 doses	n (%)				
Days from index vaccination to second dose	mean (sd) median Q1, Q3				
Days from second vaccination to third dose	mean (sd) median Q1, Q3				
Days from third vaccination to fourth dose	mean (sd) median Q1, Q3				
Other vaccines received during observation period					
Any vaccination during observation period	n (%)				
vaccine 1	n (%)				
vaccine 2	n (%)				
Other*	n (%)				
Other vaccines received concomitantly with subsequent MenACWY-CRM dose					
Any vaccination received concomitantly	n (%)				
vaccine 1	n (%)				
vaccine 2	n (%)				
Other*	n (%)				
Completed 6-month observation period following last dose	n (%)				
Duration of observation period (months) with censoring	mean (sd) median Q1, Q3 (min - max)				

* Includes all vaccines with less than 10 recipients during observation period

† Any cell with count >0 but less than 3 is presented as "<<"

N/A = Not Applicable

Table 4a: Summary of Hospitalization and Emergency Room Visit Event Identification and Review

Event	Automated Algorithm			Physician Review			Total Events for Analysis (g=a-b-e-f)
	Potential events identified (a)	Excluded events based on pre-existing condition (b)	Events remaining from automated identification (c=a-b)	Events confirmed (d)	Events refuted (e)	Confirmed events with diagnosis determined to be prior to index vaccination (f)	
Hospitalization only							
Emergency department only							
Emergency department and hospitalization							
Number of recipients experiencing a single hospitalization or emergency encounter							

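### The 'Per event' population in SAP section 8 removes children from Tables 4 and 5, while sections 5.1 and 5.2 and the Table 4 shells remove only events

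*SAP*

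**What the plan says.** The table list in SAP v2.0 section 8 labels Tables 4, 5 and 6 'Per event', and the footnote defines the label: "Per event will include all recipients with no history of that event prior to the first MenACWY-CRM dose". Draft v1.2 has the same text. The list separates Table 5a from 5b in its strata column but not in its population column, so the label covers both.

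The Definitions allow two kinds of event: "Events are classified on an encounter level and a diagnosis level". At encounter level, "an inpatient admission, emergency department (ED) visit, or an ED visit resulting in an inpatient admission will each be treated as a single event".

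Four other places bear on who and what is counted:

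- **SAP 5.1, encounters.** "Encounters will be considered pre-existing if all diagnoses made during the encounter are present in the medical record prior to the first dose" of vaccine.
- **SAP 5.1, diagnoses.** "A diagnosis will be excluded as pre-existing if the same ICD diagnosis code appears in any medical setting" before the first dose.
- **Table shells 4a and 4b.** Column a counts potential events and column b counts those excluded as pre-existing. Column b is subtracted to reach the analysed total (g=a-b-e-f in 4a, i=a-b-e-f-g in 4b).
- **SAP 5.2.** The rate is captured events over all person-time following doses, with no condition on history.

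Protocol 9.2.3 sets no exclusion criteria for the study population.

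**The concern.** The footnote acts on recipients; section 5.1 acts on events. A child with an old diagnosis stays in the table under 5.1 and loses only the matching event. Under the footnote the child leaves that row, together with the person-time and any other event that would have counted there.

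Two outputs are affected. Table 4 is meant to show how many identified events were set aside as pre-existing, which is only possible if children with a history are in it. Table 5a carries the emergency and hospitalization rates named in the study objective. If the footnote is followed, those rates describe a selected part of the recipients, and the report would not show it. Section 5.4 plans no sensitivity analysis. Under section 9.2 the second programmer reviews all code but independently extracts only the vaccination data, and would work from the same conflicting text.

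**Working it through.** **1. The plan's own figures.** The only numerical table in the SAP is the expected confidence intervals in section 3.2. With x = rate × N × 1 person-year, the exact Poisson limits are χ²(0.025; 2x)/2 and χ²(0.975; 2x+2)/2, divided by the person-years. Ten of the 12 cells reproduce to the printed decimal, for example 81.4-121.6 at N=100 and 100 per 100 person-years. The other two, both at N=50, differ by 0.1 at one limit (9.3 against 9.4; 3.2 against 3.3). The method is confirmed and is reused in step 4.

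**2. Table 4b.** On a specific-diagnosis row, the footnote and the 5.1 rule use the same criterion: that diagnosis recorded before the first dose. Once children who meet it are out of the table, none of their diagnoses can appear in column b. Column b is zero by construction on those rows.

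**3. Tables 4a and 5a.** An encounter row has no single diagnosis, so 'that event' has two possible meanings. Take four children with one post-dose emergency visit each:

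- A: no earlier emergency visit; same code seen earlier as an outpatient
- B: earlier emergency visit for a different code
- C: earlier emergency visit for the same code
- D: no history

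| Rule | Children kept | Column a | Column b | Events analysed |
|---|---|---|---|---|
| 5.1 with 5.2 | A, B, C, D | 4 | 2 (A, C) | 2 |
| Footnote, event = encounter type | A, D | 2 | 1 (A) | 1 |
| Footnote, event = encounter pre-existing under 5.1 | B, D | 2 | 0 | 2 |

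Neither child-level reading gives the column b of 5.1, and both halve the denominator. At one person-year each, the rates are 2/4, 1/2 and 2/2, that is 50, 50 and 100 per 100 person-years. The example shows that the readings differ; it does not predict a direction. In general the rate falls if the children removed have more countable encounters per person-year than those who stay, and rises if they have fewer.

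**4. Precision only.** SAP 3.2 expects 60-100 high-risk children; assume that all are vaccinated. The share with the relevant history is not in the documents, so 20% to 80% is assumed. Intervals are at 100 events per 100 person-years:

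| Share removed | From N=60 | 95% CI | From N=100 | 95% CI |
|---|---|---|---|---|
| 0% | 60 | 76.3-128.7 | 100 | 81.4-121.6 |
| 20% | 48 | 73.7-132.6 | 80 | 79.3-124.5 |
| 40% | 36 | 70.0-138.4 | 60 | 76.3-128.7 |
| 60% | 24 | 64.1-148.8 | 40 | 71.4-136.2 |
| 80% | 12 | 51.7-174.7 | 20 | 61.1-154.4 |

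**The case against.** The best defence is that the detailed text already settles the matter. SAP 3.3.3 matches history by ICD code, 5.1 has its own rule for encounters, the shells carry the subtraction, and 5.2 fixes the denominator. Nothing in the SAP treats an earlier emergency visit as making a later, unrelated one pre-existing. A programmer working from the shells would fill column b and keep every child. The study is descriptive and tests no hypothesis.

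Much of this stands. It probably reflects the intention, and the ICD-code matching weighs against reading 'that event' as the encounter type. It does not remove the conflict: the footnote is an explicit population rule in the approved SAP, it speaks of recipients, and nothing says that section 5 overrides section 8.

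Three stronger inferences are tempting, and the documents do not support them:

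- **That column b of Table 4a is empty and every child with an earlier emergency visit or admission leaves Table 5a.** These need different readings. On the encounter-type reading column b is undercounted but not empty, because an earlier code may be outpatient only (child A). On the other reading it is empty, but a child with an earlier unrelated visit stays (child B). Even on the encounter-type reading the loss is row by row: a child whose only history is an emergency visit without admission leaves only the emergency-only row.
- **That birth stays would empty the hospitalization rows.** Protocol 9.2.2 counts deliveries. It does not say that a birth stay is recorded as an admission of the child.
- **That the understatement of the rates can be given as a percentage.** It would need the share of children with a history and their relative rate of later encounters, row by row. Neither is in the documents.

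**Conclusion.** The concern holds as a contradiction between section 8 and sections 5.1 and 5.2 and the Table 4 shells. Column b of Table 4b is zero on the specific-diagnosis rows if the footnote is followed. Column b of Table 4a is zero or undercounted, depending on an undefined term. On either reading Table 5a loses children and person-time that section 5.2 includes, provided that some recipients have the history in question.

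The rates would be too low if children who used hospital care before vaccination also have more countable encounters afterwards. That is plausible where vaccination is for conditions such as sickle cell disease, but it is an assumption, and the size of any shift cannot be computed. The intervals above show lost precision only and rest on assumed shares. The text should be corrected before the tables are programmed.

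**What to change.** In SAP section 8, set the population of Tables 4a, 4b and 5a to all recipients. State that events are excluded only by the section 5.1 rules and that the denominator is the one in section 5.2.

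Keep the no-history population only for the single-diagnosis rows of Table 5b and for Table 6. Section 5.2 must change with it, because its total person-time includes children whom those Table 5b rows would leave out: amend it so that the person-time for those rows comes from the same children. State the population and person-time for the diagnosis-grouping rows too, including whether history there means the same code or any code in the group.

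The cost is a few entries and the footnote in section 8, and a short addition to section 5.2. No new data are needed.

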9. QUALITY CONTROL

9.1 Data Management

Data for this study will include vaccination, demographics, membership, utilization, death, and data from the identification and validation of serious medically-attended events that may occur in the six months following vaccination. The contents of the various datasets are specified separately in a data dictionary, which will be provided with the relevant SAS programming.

9.2 Data Quality Checks

Range checks and general frequency tables will be produced such that missing values, outliers, and inappropriate or abnormal values will be identified. Comparisons between date of birth, date of death, event dates and vaccination dates will be made. All data will be checked for duplicate records.

A record of data quality problems and resolutions will be kept in the form of an Excel spreadsheet or other method appropriate to the circumstances (e.g. commented code, detailed correspondence). All inconsistencies and/or data quality issues will be documented. Revisions will be noted in order to capture the change made, the change date, identification of the individual making the change, as well as noting any further actions to be taken to identify and/or resolve additional data quality problems of this type.

All programming will be reviewed by a second programmer. Additionally, prior to reviewing the original programming, the second programmer will independently extract vaccination data. The results of the original and validation programming will be compared and any discrepancies will be investigated. A report will be created, listing discrepancies, their causes, and any action taken to resolve them. It is expected that there may be a small number of discrepancies due to a difference in the date on which the original and validation programs are run, as they are pulling from live databases which are updated regularly. If this cause is suspected, both programs may be run again on the same date as a means to eliminate this potential cause of discrepancies.

